3.2 Study Treatment

The treatment to be used in this trial is outlined below in Table 1, further details can be found in Section 6 of the study protocol.

Table 1: Trial Treatment

Drug	Dose/ Potency	Dose Frequency	Route of Administration	Regimen/Treatment Period	Use
Pembrolizumab	200 mg	Q3W	IV infusion	Day 1 of each 3 week cycle	Experimental

Trial treatment should begin on the day of study entry (screening and consent completed) or as close as possible to the date on which treatment is allocated.

3.3 Study Population

This trial will be performed at three investigational sites in England, and recruit patients who were histologically confirmed with cancer of an unknown primary. See full eligibility criteria below.

3.4 Eligibility Criteria

Inclusion Criteria

Patients who meet all of the following inclusion criteria will be considered eligible for this study:

1. Be willing and able to provide written informed consent/assent for the trial.
2. Be ≥ 18 years of age on day of signing informed consent.
3. Have measurable disease based on RECIST 1.1.
4. Be willing to provide consent for archival tumour (in the form of formalin fixed paraffin embedded (FFPE) block) or fresh tumour material (if judged technically feasible by radiologist) is mandatory for diagnosis and biomarker analysis.
5. Have a performance status of 0-2 on the ECOG Performance Scale.
6. Have had at least one prior line / regimen of chemotherapy appropriate for CUP (at least 2 cycles). Either did not have a RECIST response to first-line chemotherapy or progressing after an initial response, or are treatment intolerant to first-line chemotherapy due to unacceptable toxicity.
7. Adequate organ and bone marrow function (all screening tests should be performed within 10 days of treatment initiation):
 - a. Absolute neutrophil count (ANC) $\geq 1.5 \times 10^9/L$
 - b. Platelets $\geq 100 \times 10^9/L$
 - c. Haemoglobin ≥ 9 g/dL (≥ 90 g/L) without transfusion or EPO dependency (within 7 days of assessment)
 - d. Serum creatinine $\leq 1.5 \times$ Upper Limit of Normal (ULN) or Creatinine clearance* ≥ 60 mL/min for patients with creatinine levels $> 1.5 \times$ ULN
* Creatinine clearance should be calculated per institutional standard
 - e. Serum total bilirubin $\leq 1.5 \times$ ULN or direct bilirubin \leq ULN for patients with total bilirubin levels $> 1.5 \times$ ULN
 - f. Aspartate aminotransferase [AST] $\leq 2.5 \times$ ULN ($< 5 \times$ ULN if liver metastases are present)
 - g. Alanine aminotransferase [ALT] $\leq 2.5 \times$ ULN ($< 5 \times$ ULN if liver metastases are present)
 - h. Albumin ≥ 2.5 g/dL
 - i. International Normalized Ratio (INR) or Prothrombin Time (PT) $\leq 1.5 \times$ ULN (unless subject is receiving anticoagulant therapy as long as PT or PTT is within therapeutic range of intended use of anticoagulants)

- j. Activated Partial Thromboplastin Time (APTT) $\leq 1.5 \times \text{ULN}$ (unless subject is receiving anticoagulant therapy as long as PT or PTT is within therapeutic range of intended use of anticoagulants).
- 8. Female subject of childbearing potential should have a mandatory negative serum pregnancy within 72 hours prior to receiving the first dose of study medication.
- 9. Female subjects of childbearing potential must be willing to use an adequate method of contraception as outlined in Section 6.9.2 – Contraception, for the course of the study through 120 days after the last dose of study medication. Note: Abstinence is acceptable if this is the usual lifestyle and preferred contraception for the subject.
- 10. Male subjects of childbearing potential must agree to use an adequate method of contraception as outlined in Section 6.9.2 - Contraception, starting with the first dose of study therapy through 120 days after the last dose of study therapy. Note: Abstinence is acceptable if this is the usual lifestyle and preferred contraception for the subject.

Exclusion Criteria

Patients who meet any of the following exclusion criteria will not be eligible for this study:

1. Is currently participating and receiving study therapy or has participated in a study of an investigational agent and received study therapy or used an investigational device within 4 weeks of the first dose of treatment
2. Has a diagnosis of immunodeficiency or is receiving systemic steroid therapy or any other form of immunosuppressive therapy within 7 days prior to the first dose of trial treatment
3. Has a known history of active TB (Bacillus Tuberculosis)
4. Hypersensitivity to pembrolizumab or any of its excipients
5. Has had a prior anti-cancer monoclonal antibody (mAb) within 4 weeks prior to study Day 1 or who has not recovered (i.e., \leq Grade 1 or at baseline) from adverse events due to agents administered more than 4 weeks earlier
6. Has had prior chemotherapy, targeted small molecule therapy, or radiation therapy within 2 weeks prior to study Day 1 or who has not recovered (i.e., \leq Grade 1 or at baseline) from adverse events due to a previously administered agent

- Note: Subjects with \leq Grade 2 neuropathy are an exception to this criterion and may qualify for the study.
 - Note: If subject received major surgery, they must have recovered adequately from the toxicity and/or complications from the intervention prior to starting therapy.
7. Has a known additional malignancy that is progressing or requires active treatment. Exceptions include basal cell carcinoma of the skin or squamous cell carcinoma of the skin that has undergone potentially curative therapy or in situ cervical cancer.
 8. Has known active central nervous system (CNS) metastases and/or carcinomatous meningitis. Subjects with previously treated brain metastases may participate provided they are stable (without evidence of progression by imaging for at least four weeks prior to the first dose of trial treatment and any neurologic symptoms have returned to baseline), have no evidence of new or enlarging brain metastases, and are not using steroids for at least 7 days prior to trial treatment. This exception does not include carcinomatous meningitis which is excluded regardless of clinical stability.
 9. Has active autoimmune disease that has required systemic treatment in the past 2 years (i.e. with use of disease modifying agents, corticosteroids or immunosuppressive drugs). Replacement therapy (e.g., thyroxine, insulin, or physiologic corticosteroid replacement therapy for adrenal or pituitary insufficiency, etc.) is not considered a form of systemic treatment.
 10. Has a history of (non-infectious) pneumonitis that required steroids or has current pneumonitis
 11. Has an active infection requiring systemic therapy
 12. Has a history or current evidence of any condition, therapy, or laboratory abnormality that might confound the results of the trial, interfere with the subject's participation for the full duration of the trial, or is not in the best interest of the subject to participate, in the opinion of the treating investigator
 13. Has known psychiatric or substance abuse disorders that would interfere with cooperation with the requirements of the trial

14. Is pregnant or breastfeeding, or expecting to conceive or father children within the projected duration of the trial, starting with the pre-screening or screening visit through 120 days after the last dose of trial treatment
15. Has received prior therapy with an anti-PD-1, anti-PD-L1, or anti-PD-L2 agent
16. Has a known history of Human Immunodeficiency Virus (HIV) (HIV 1/2 antibodies)
17. Has known active Hepatitis B (e.g., HBsAg reactive) or Hepatitis C (e.g., HCV RNA [qualitative] is detected)
18. Has received a live vaccine within 30 days of planned start of study therapy. Note: Seasonal influenza vaccines for injection are generally inactivated flu vaccines and are allowed; however intranasal influenza vaccines (e.g., Flu-Mist®) are live attenuated vaccines, and are not allowed.

3.5 Sample Size

1) In the first cohort 20 second-line (or more) patients will be accrued; if no responses or benefit is observed in 20 assessable patients, accrual of the whole trial will stop at this point. “Assessable” is defined as patients who have had at least 2 cycles of Pembrolizumab and are assessable for response at a minimum of 6 weeks post-study start.

2) The study statistics were originally modelled on the UK CUP-ONE trial based on the primary study endpoint of response in cohort 2.

An interim futility analysis was originally pre-planned after recruiting 24 (out of 57) patients in Cohort 2 and a final analysis after 77 participants completed the study (20 for Cohort 1 and 57 for Cohort 2). ≥1 documented response in Cohort 1 was achieved in May 2020, enabling Cohort 2 to open and Cohort 1 to close once sufficient evaluable participants had been enrolled. Due to the unexpected challenges recruiting study participants outlined in the Trial Summary and sections 1.3.1 and 3.1, particularly for Cohort 2, Cohort 1 was reopened and expanded and the initial version 7.0 of the protocol has formally closed Cohort 2 with approval from the TMG, MSD and combined

TSC/IDMC. Cohort 1 (pre-treated patients) remains a crucial area of unmet need with no standard of care treatment existing.

The sample size has thus been recalculated to accommodate the shift of focus to assessing PFS and OS in Cohort 1 and complete removal of Cohort 2. The sample sizes were recalculated based on the Brookmeyer-Crowley test for median survival time (Brookmeyer R and Crowley JJ. A confidence interval for the median survival time. Biometrics. 1982: 38, 29-41).

Assuming a historic null PFS of 2 months and an alternative PFS of 4 months, the minimum required sample size to determine the median PFS for the study cohort is 46 (at 0.05 level of significance, one-sided, 90% power). For the OS, assuming a null OS of 4 months and an alternative OS of 7 months, the required minimum sample size is 67 with the same level of significance and power. Therefore, the final sample size needed to determine both the median PFS and OS is 67 (the higher sample size). In the event that this sample size will be difficult to recruit within the additional accrual period of 12 months, a sample size of 31 will still be able determine the median PFS and 45 the median OS with a power of 80%.

Power	Null Median Survival	Alternative Median Survival	Min N
0.80	2 months PFS	4 months	31
0.90	2 months	4 months	46
0.80	4 months OS	6 months	83
0.80	4 months	7 months	45
0.90	4 months	6 months	122
0.90	4 months	7 months	67

The study will therefore aim to recruit between 31 and 67 patients to Cohort 1 within the allotted study period. This sample size range is estimated to have a power of 80% to 90% in determining the PFS and/or the OS of the study cohort.

As for DCR, the minimum range of this sample size (i.e. 31) would require ≥ 10 DCR to recommend Pembrolizumab for further evaluation, assuming an unacceptable DCR of $\leq 20\%$ (P0) vs the desired rate of $\geq 40\%$ (P1). This Fleming single-stage design would provide a one-sided alpha of 8% and a power of 86%. Different simulations for the minimum DCR needed ($H_0: P \leq 0.2$ vs $H_1: P \geq 0.4$) given a one-sided alpha $\leq 10\%$ and power $\geq 80\%$ are presented below:

Power	N	Alpha	Minimum DCR needed
0.80	35	0.03	12
0.86	31	0.08	10
0.90	47	0.04	15
0.91	42	0.06	13
0.91	36	0.09	11

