## 2 OBJECTIVES AND HYPOTHESIS(ES)

### 2.1 Primary Objectives and Hypothesis

#### Objectives:

- Overall response rates by immune-related (irRECIST) and RECIST criteria:
  - Disease Control Rate (DCR), Overall Survival (OS) & Progression Free Survival (PFS).

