### 8.2 Sample size, power considerations and planned recruitment rate

An interim futility analysis was originally pre-planned after recruiting 24 (out of 57) patients in Cohort 2 and a final analysis after 77 participants completed the study (20 for Cohort 1 and 57 for Cohort 2).  $\geq 1$  documented response in Cohort 1 was achieved in May 2020, enabling Cohort 2 to open and Cohort 1 to close once sufficient evaluable participants had been enrolled. Due to the unexpected challenges recruiting study participants outlined in the Trial Summary and sections 1.3.1 and 3.1, particularly for Cohort 2, Cohort 1 was reopened and expanded. Version 7.0 of the protocol has formally closed Cohort 2 with approval from the TMG, MSD and combined TSC/IDMC. Cohort 1 (pre-treated patients) remains a crucial area of unmet need with no standard of care treatment existing.

The study statistics were originally modelled on the UK CUP-ONE trial based on the primary study end-point of response in cohort 2.

The sample size has thus been recalculated to accommodate the shift of focus to assessing PFS and OS in Cohort 1 and complete removal of Cohort 2. The sample sizes were recalculated based on the Brookmeyer-Crowley test for median survival time (Brookmeyer R and Crowley JJ. A confidence interval for the median survival time. Biometrics. 1982: 38, 29-41).

CUPem	C/37/2017	Imperial College London	V7.0, 08.12.2021
-------	-----------	----------------------------	------------------

Assuming a historic null PFS of 2 months and an alternative PFS of 4 months, the minimum required sample size to determine the median PFS for the study cohort is 46 (at 0.05 level of significance, one-sided, 90% power). For the OS, assuming a null OS of 4 months and an alternative OS of 7 months, the required minimum sample size is 67 with the same level of significance and power. Therefore, the final sample size needed to determine both the median PFS and OS is 67 (the higher sample size). In the event that this sample size will be difficult to recruit within the additional accrual period of 12 months, a sample size of 31 will still be able determine the median PFS and 45 the median OS with a power of 80%.

Power Size	Null Median Survival	Alternative Median Survival	Min Sample Size
0.80	2 months PFS	4 months	31
0.90	2 months	4 months	46
0.80	4 months OS	6 months	83
0.80	4 months	7 months	45
0.90	4 months	6 months	122
0.90	4 months	7 months	67

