2.1 Primary Objectives

Objectives:

Overall response rates by immune-related (irRECIST) and RECIST criteria:

Disease Control Rate (DCR), Overall Survival (OS) & Progression Free Survival (PFS).

Hypothesis:

Pembrolizumab has Efficacy in CUP:

- as a second-line treatment in terms of Response which translates into improved PFS and OS.
- and treatment leads to rapid improvement in QOL in high metastatic disease burden.

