5.10 Exploratory Variables

Exploratory variables include genomic biomarkers predictive of immune response to Pembrolizumab. Genomic sequencing will be done within the 100K-genome project, the data from which can be linked to this and other CUP trials. This is not costed in this application and the analysis will not be included in this statistical analysis plan.

6 Statistical Methodology

The study data will be summarised using standard descriptive methods by cohort and as combined data. Histograms and box-plots will be used to assess the distributional assumptions and to check for possible outliers. Mathematical transformations will be applied, where appropriate, in order to render variables normally distributed. Continuous variables that follow an approximately normal distribution will be summarised using the mean and standard deviation (StDev). Skewed continuous variables will be summarised using the median and inter-quartile range (IQR). Categorical variables (binary, ordered and multinomial) will be presented in terms of frequencies and percentages.

The primary outcome and secondary outcome will be tested using a two-tailed hypothesis test with a 5% significant level.

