6.3 Primary Efficacy Analysis

The overall response rate will be calculated as the proportion of patients who have a complete response (CR) or partial response (PR) to treatment as assessed by the objective tumour response criteria: RECIST v1.1 **or** immune-related (irRECIST). The response rate and its 95% confidence interval (CI) will be presented for each cohort. As previously described, the response rate is the primary efficacy variable that will be used to decide whether the study will stop or continue accrual in both cohorts.

Disease Control Rate (DCR) will be calculated for each cohort as the proportion of patients in whom the best overall response is determined as complete response (CR), partial response (PR) or stable disease (SD) for at least 12 weeks in either RECIST **or** irRECIST criteria.

The Overall Survival (OS) and Progression Free Survival (PFS) will be summarized descriptively using the median and Kaplan-Meier graph for each cohort.

The Quality of Life (QOL) in each cohort will be assessed using mean or median scores from the EORTC QLQ-C30 (version 3) questionnaire administered at baseline, after 3 months and then at discontinuation of study treatment. The QOL scores between visit dates will be compared using Repeated Measures ANOVA or Friedman's Test on the per-protocol population who completed the baseline and at least one follow-up QoL assessment. The type of statistical test to be used will depend on the characteristic of the data distribution. Adjustment for multiple testing will be applied. The Tukey post-hoc method or the Wilcoxon signed-rank test will be used for pairwise comparisons. Profile plots and longitudinal plots will also be presented.

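### The protocol and SAP give conflicting statements of which endpoint decides the trial, and no rule for when PFS, OS and DCR disagree

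*SAP*

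**What the plan says.** Protocol 2.1 and SAP 2.1 set one primary objective: overall response by irRECIST and RECIST, with "Disease Control Rate (DCR), Overall Survival (OS) & Progression Free Survival (PFS") beneath it. The primary hypothesis also covers quality of life ("and treatment leads to rapid improvement in QOL in high metastatic disease burden"), and SAP 5.1 lists quality of life under the primary efficacy endpoint. The later sections then diverge:

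- **Protocol 8.2 and SAP 3.5** recalculate the sample size for "the shift of focus to assessing PFS and OS in Cohort 1 and complete removal of Cohort 2". PFS is 2 against 4 months and OS is 4 against 7 months, both "at 0.05 level of significance, one-sided, 90% power". The conclusion on power is "This sample size range is estimated to have a power of 80% to 90% in determining the PFS and/or the OS of the study cohort".
- **SAP 3.5** adds a DCR rule. At N=31, ten or more patients with disease control lead to a recommendation for further evaluation (20% against 40%, one-sided alpha 8%, power 86%).
- **SAP section 6**, opening text: "The primary outcome and secondary outcome will be tested using a two-tailed hypothesis test with a 5% significant level". The outcome is not named.
- **SAP 6.3** says "the response rate is the primary efficacy variable that will be used to decide whether the study will stop or continue accrual" in both cohorts. It gives response a 95% confidence interval but no null rate. OS and PFS are summarised by median and Kaplan-Meier plot, with no test against the null medians. Multiplicity adjustment is mentioned only for quality of life.

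**The concern.** An analyst following these sections could not say which result makes the trial positive. The sample-size section implies tests of PFS and OS, and the analysis section does not plan them. DCR has a stand-alone threshold that nothing ranks against the survival endpoints. One section is one-sided and the other two-tailed.

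Two things are at stake. If any single success may be presented as the primary result, the error rate of the conclusion is not that of any one test. If the endpoints disagree, the choice between them would be made after the data are seen.

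**Working it through.** **1. The plan's own figures.** With exponential survival and a one-sample test of the survival probability at the null median, p1 = 0.5^(m0/m1) and n = [(1.645×0.5 + z_b×√(p1(1−p1))) / (p1−0.5)]².

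- PFS, 2 against 4 months: p1 = 0.707. At 90% power n = 46.1 (plan: 46).
- OS, 4 against 7 months: p1 = 0.673. At 90% power n = 67.8 (plan: 67).
- At 80% power the same formula gives 33.9 and 49.5, against the plan's 31 and 45. Those rows are therefore somewhat optimistic by this method.
- DCR, at least 10 of 31, exact binomial: alpha 7.46% and power 85.7% (plan: 8% and 86%).

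**2. Power by endpoint and N** (same formula, one-sided 5%):

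| N | PFS 2 v 4 | OS 4 v 7 |
|---|---|---|
| 31 | 77% (plan 80%) | 62% |
| 45 | 89% | 76% (plan 80%) |
| 46 | 90% (plan 90%) | 77% |
| 67 | 97% | 90% (plan 90%) |

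So at N=31 the 80% end of the stated range is claimed for PFS only.

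**3. False-positive chance if any one of PFS, OS or DCR counts, N=31.** Only these three have stated nulls. The documents give no correlation between them, so a common correlation ρ of 0 to 0.8 is assumed. The chance is 1 − ∫φ(x) ∏Φ[(z_i + √ρ·x)/√(1−ρ)] dx, where z_i is the critical value of test i.

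At ρ=0 this reduces to 1 − 0.95×0.95×0.9254 = 16.5% at the one-sided levels. With PFS and OS at two-tailed 5% (2.5% in the favourable direction) it is 1 − 0.975×0.975×0.9254 = 12.0%.

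| ρ | PFS and OS one-sided 5%, DCR 7.46% | PFS and OS two-tailed 5%, DCR 7.46% | PFS or OS only, one-sided / two-tailed |
|---|---|---|---|
| 0 | 16.5% | 12.0% | 9.8% / 4.9% |
| 0.5 | 13.6% | 10.4% | 8.8% / 4.5% |
| 0.8 | 10.8% | 8.6% | 7.5% / 3.9% |

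A patient-level simulation at N=31, with DCR nested in PFS and DCR held at its 20% null, gives 12.9% down to 11.4% as the PFS–OS correlation rises from 0 to 0.9.

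**4. Are the nulls consistent?** "Assuming a historic null PFS of 2 months and an alternative PFS of 4 months" sets the PFS null. Twelve weeks is 84/30.44 = 2.76 months. With exponential PFS and a 2-month median, 0.5^(2.76/2) = 38% are progression-free at 12 weeks, close to the DCR alternative of 40% and well above its null of 20%. If all of those patients counted as disease control, at least 10 of 31 would occur about 81% of the time. The PFS and DCR nulls therefore cannot both hold under this model, and the table in step 3 is indicative only.

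**5. Disagreement if the drug works as assumed, N=31.** Powers: PFS 80% (plan), OS 62% (step 2), DCR 85.7%. At ρ=0: 1 − 0.80×0.62×0.857 − 0.20×0.38×0.143 = 56%. At ρ=0.5 it is 42%, and at ρ=0.8 it is 31%.

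**The case against.** The trial summary labels the study hypothesis generating, and the design section speaks of preliminary efficacy, so strict familywise control is not obligatory. SAP 6.3 plans no test of PFS or OS, so it is not established that several routes each spend alpha. The and/or sentence concerns power, and elsewhere SAP 3.5 takes N=67 as the number for both medians. If both had to succeed, the joint error would be below 5%. At two-tailed 5%, PFS and OS alone stay just under 5%, and most of the remainder is DCR's disclosed alpha.

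These points stand, and they limit the claim. Three stronger readings are tempting, but the documents do not support them:

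- **A 5% overall rate inflated to about 14% across five endpoints.** No section claims an overall 5%. Response has no null, and quality of life is a within-patient comparison with its own adjustment. The arithmetic covers three endpoints and assumes that any success counts.
- **Response rate as a rival final endpoint.** The sentence in SAP 6.3 refers to stopping or continuing accrual in both cohorts. That gate was passed in May 2020 and Cohort 2 is closed, so this is leftover text.
- **No decision rule at all.** DCR has an explicit threshold. What is missing is its rank against PFS and OS.

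The exploratory label does not remove the core problem, because the plan sets powered nulls and a go rule and its sections contradict each other.

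**Conclusion.** The concern holds as a contradiction between sections, not as a broken promise of 5% error. The deciding endpoint, its null and its sidedness cannot be read from the documents.

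If any one of PFS, OS or DCR counts as success, the false-positive chance at N=31 is about 11% to 17% at the one-sided levels, or about 9% to 12% with PFS and OS two-tailed. This rests on an assumed correlation of 0 to 0.8 and on nulls that are not fully consistent with each other. The disagreement figure of roughly 30% to 55% does not depend on how success is defined. It does use the minimum N, the plan's 80% for PFS and a derived 62% for OS.

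For a hypothesis-generating trial this is not a fatal flaw. It should be settled before analysis, since an order chosen afterwards protects nothing.

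**What to change.** Before analysis, name one primary contrast with its null and sidedness in SAP 5.1, SAP 6.3 and protocol 8.2, and make SAP section 6 and the analysis text in SAP 6.3 match it.

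- **Primary.** PFS against the 2-month null at one-sided 5% is the natural choice, because it is the only survival endpoint with a claimed 80% power at N=31. OS is an option only if N reaches at least 45. The choice is the sponsor's.
- **Other endpoints.** Label them secondary or supportive, with confidence intervals. Keep the DCR rule as a supportive go criterion at its stated 8% alpha.
- **Clean-up.** Remove the leftover response-rate accrual sentence from SAP 6.3. Replace the and/or sentence with the power for each endpoint at each N.

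This needs wording only and no extra patients. The main cost is that a success on a non-primary endpoint alone can no longer be called a positive primary result. Sidedness also matters: at two-tailed 5%, PFS power at N=31 falls from 77% to 65% by the formula above. A PFS primary also depends on scan timing. The first planned scan, at 12 weeks (2.76 months), falls after the 2-month null median, so the SAP should say how progression is dated.

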5.1 Primary Efficacy Endpoint

The overall response to treatment is assessed using RECIST v1.1 and immune-related (irRECIST). Appendices A and B in the protocol present the guidelines for evaluation of objective tumour response Using RECIST 1.1 (Response Evaluation Criteria in Solid Tumours) or immune-related RECIST. The disease control rate will be calculated.

Disease Control Rate (DCR) - is defined as the proportion of patients in whom the best overall response is determined as complete response (CR), partial response (PR) or stable disease (SD) for at least 12 weeks in either RECIST or irRECIST criteria.

Overall Survival (OS) - defined as the length of time from study enrolment until death, withdrawal of consent, last follow-up date if lost to follow-up or the end of the study, whichever occurs first.

Progression Free Survival (PFS) – is defined as the length of time from study enrolment to first evidence of progressive disease identified at follow-up or confirmed disease progression at the end of the trial or death. Patients will be censored at the last follow-up date if they are lost to follow-up, withdrawn from the study or have not progressed at the end of study. Median PFS and its 95% confidence interval will be reported. Kaplan-Meier survival curves will also be plotted.

Quality of Life (QOL) is measured as scores from the EORTC QLQ-C30 version 3 questionnaire which will be administered at baseline, after 3 months and then at discontinuation of study treatment.

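### The DCR go rule in SAP 3.5 (at least 10 of 31; 20% vs 40%) is not calibrated to the PFS hypotheses (median 2 vs 4 months) for the same cohort

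*SAP*

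**What the plan says.** SAP 3.5 sets two sets of hypotheses for Cohort 1.

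- PFS: "Assuming a historic null PFS of 2 months and an alternative PFS of 4 months", with 46 patients "at 0.05 level of significance, one-sided, 90% power" and 31 for 80% power. On method: "The sample sizes were recalculated based on the Brookmeyer-Crowley test for median survival time".
- DCR: "the minimum range of this sample size (i.e. 31) would require" at least 10 "DCR to recommend Pembrolizumab for further evaluation, assuming an unacceptable DCR of" 20% or less, with 40% or more as the desired rate. "This Fleming single-stage design would provide a one-sided alpha of 8% and a power of 86" per cent. Four further combinations are tabulated: 12/35, 15/47, 13/42 and 11/36.

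SAP 5.1 counts a patient as controlled on CR, PR "or stable disease (SD) for at least 12 weeks in either RECIST or irRECIST criteria". The first on-study scan is at 12 weeks (SAP Table 2 and its footnote g; Protocol 5.9.15) or 3 months (Protocol and SAP 3.1). Protocol Appendix A times stable disease from the start of treatment. Protocol 8.3 classes progression before the 12-week scan as treatment failure.

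Neither document gives a source for 20% and 40% or ties them to the 2- and 4-month medians. The DCR rule is in the SAP only; Protocol 8.2 has no DCR threshold.

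**The concern.** A patient who progresses before the first scan fails. One who is stable or responding at about 12 weeks is controlled. DCR is therefore nearly the proportion progression-free at 12 weeks, which is a point on the PFS curve whose median is tested in the same section. If the two sets of hypotheses describe one inactive drug and one active drug, the DCR rates should be roughly what the PFS medians imply at 12 weeks. They appear not to be: the desired DCR sits about where the PFS null would put it.

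This matters because the DCR rule is the only numerical criterion in either document for recommending further evaluation, while SAP 6.3 summarises PFS and OS by medians and Kaplan-Meier curves. A drug no better than the plan's own historic PFS could be recommended under a nominal 8% error rate that does not apply to it.

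**Working it through.** **Inputs.** n = 31 with cut-off 10, P0 = 0.20 and P1 = 0.40, medians of 2 and 4 months (all SAP 3.5). The horizon is 12 weeks = 84/30.4375 = 2.76 months.

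**1. The plan's own DCR figures.** Exact binomial: P(X ≥ 10 | 31, 0.20) = 0.0746 and P(X ≥ 10 | 31, 0.40) = 0.857. The power matches. The alpha is 7.5%, printed as 8%. The other four rows reproduce to the printed digits.

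**2. The survival shape implied by the plan's PFS sample sizes.** The documents name no distribution. Take a one-sample test of S(t) at the null median, one-sided 0.05. If PFS is exponential with a 4-month median, S1 at 2 months = 0.5^(2/4) = 0.707, and

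n = [(1.645 × 0.5 + z_power × √(0.707 × 0.293)) / (0.707 − 0.5)]²

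This gives 33.9 at 80% power and 46.1 at 90%. On the complementary log-log scale the results are 32.2 and 47.0. The plan states 31 and 46. Solving for the Weibull shape that returns each of the six stated PFS and OS sample sizes gives 1.00 to 1.06, which is close to exponential.

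**3. DCR at the PFS hypotheses, exponential.**

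- Median 2 months: 0.5^(2.76/2) = 0.384
- Median 4 months: 0.5^(2.76/4) = 0.620
- Median implied by a 20% DCR: 2.76 × ln 2 / ln 5 = 1.19 months
- Median implied by a 40% DCR: 2.76 × ln 2 / ln 2.5 = 2.09 months

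**4. Pass probability at the 2-month null.** P(X ≥ 10 | 31, 0.384) = 0.81. The other listed rules pass as follows:

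| Rule | Pass probability at PFS null | Printed alpha |
|---|---|---|
| 12/35 | 75% | 3% |
| 15/47 | 86% | 4% |
| 13/42 | 88% | 6% |
| 11/36 | 87% | 9% |

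**5. Sensitivity of the 10/31 rule at a 2-month median.**

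| Assumption | DCR | Pass probability |
|---|---|---|
| Exponential, 12 weeks, all evaluable | 38.4% | 81% |
| Shapes 1.00 to 1.06 (step 2) | about 38% | 79% to 81% |
| Exponential, horizon of 3 months | 35.4% | 70% |
| 10% non-evaluable, counted as failures | 34.6% | 67% |
| 20% non-evaluable, counted as failures | 30.7% | 49% |
| Weibull shape 1.5 | 32.5% | 58% |
| Weibull shape 2 | 26.7% | 30% |

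A DCR of 20% at a 2-month median needs a shape of about 2.6. The same formulas would then give a PFS sample size of about 8 to 12, not 31 to 46.

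**6. Without a model.** Twelve weeks (2.76 months) comes before 4 months. A 4-month median therefore means at least 50% are progression-free at 12 weeks, whatever the curve shape, so P1 = 40% lies below what the PFS alternative implies.

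**The case against.** The strongest reply is that the SAP never says a 20% DCR and a 2-month median describe the same drug. A reader might infer that the two hypotheses contradict each other. The documents do not support that: a 2-month median does not by itself exclude a 20% DCR, a steep enough hazard reconciles them, and the binomial figures are right for the stated rates. This stands, so the point is one of calibration. Nor is there a logical clash at the alternative: H1 is written as 40% or more, and a drug with a 4-month exponential median would almost certainly pass (99.98%).

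The 81% is also conditional. It needs exponential PFS, a 12-week horizon and 31 evaluable patients. If the historic 2 months is PFS as recorded under 12-weekly imaging, silent progression first appears on the very scan that decides DCR. As an illustration, if 30% of those still event-free show progression on that scan, DCR is 0.7 × 38.4% = 27% and the pass rate is 31%. The documents do not say which kind of PFS the 2 months is. In the other direction, accepting control by either criterion can only raise DCR.

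A reader might conclude that 38% must be declared the inactive rate. That goes too far. SAP section 1 and Protocol 1.3.1 describe disease control of meaningful duration beyond first line as rare, which favours a low P0. The documents show that the two sets need reconciling, not which one is wrong.

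A reader might also infer that the ±7-day scan window makes stable disease on a slightly early scan fail the 12-week requirement. Protocol Appendix A does not support this. It runs stable disease until progression criteria are met, not to the scan date, so stable disease seen on day 80 continues past day 84 unless the patient progresses or dies in between.

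Finally, the trial calls itself hypothesis generating and the rule only recommends further evaluation. That lowers the severity but does not remove the mismatch.

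**Conclusion.** The point holds as a calibration gap and should be fixed. The rule controls error at a 20% DCR, but not at the inactive PFS that the same section assumes. Under the shape implied by the plan's own sample sizes, and with all patients evaluable, the chance of passing 10/31 at that null is about 70% to 81%, against a printed 8%. It falls to 49% with 20% non-evaluable and to 30% at Weibull shape 2. These are still well above 8%; only a shape near 2.6, which the PFS sample sizes do not fit, brings the figure down to the printed alpha.

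The conclusion rests on treating DCR as the proportion progression-free at about 12 weeks and, for the null, on near-exponential PFS, which is inferred rather than stated. The finding that the desired 40% lies below what a 4-month median implies needs only the first of these.

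**What to change.** In SAP 3.5, put the two sets of hypotheses on the same footing, in one of two ways.

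1. Derive P0 and P1 from the PFS medians: about 38.4% vs 62% under exponential PFS. Exact cut-offs at the planned sizes would be:

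| Rule | Alpha | Power |
|---|---|---|
| at least 17 of 31 | 4.7% | 84% |
| at least 24 of 46 | 4.0% | 93% |
| at least 33 of 67 | 4.6% | 99% |

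State P0 to three digits. If it is rounded to 38%, the alpha for 17/31 is 4.2%.

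2. Keep 20% and 40%, but give their source, explain how they fit with a 2-month PFS null, and state the rule's pass probability at that null. Add that a DCR pass alone does not support a recommendation when PFS fails to exceed its null.

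The cost is SAP wording, with no new data. Under the first route, or with the added condition in the second, the bar becomes less favourable to the drug.
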